6. INVESTIGATIONAL PRODUCT(S)

All investigational products to be used in this study have been manufactured, packaged and labelled by contract manufacturers for ABIVAX, according to GMP standards and are supplied to investigators free of charge.

6.1. Description of investigational treatment

The study treatment that will be administrated to subjects enrolled in this Phase IIa study consists of capsules containing ABX464 or its matching placebo given orally once daily for 56 days.

6.2. Description of investigational Product

6.2.1. Active investigational product (ABX464)

The ABX464 investigational medicinal product (IMP) is a hard gelatin capsule intended for oral administration.

For the proposed clinical trial, the IMP consists of size 01 capsules containing 50 mg of ABX464 drug substance in the form of granulate prepared with a number of common excipients (microcrystalline cellulose, polyvinylpyrrolidone, magnesium stearate and colloidal silica). It is supplied in high-density polyethylene bottles closed with high-density screw caps.

ABX464 will be manufactured by:

DELPHARM Lille SAS [name] France

Primary packaging labelling as well as Qualified Person release of the IMP are performed at the following site:

SODIA [name]

The study drug requires no specific storage conditions.

6.2.2. Placebo

The matching placebo consists of the same hard gelatin, powder-filled capsules (size 01) filled with only the same common excipients (microcrystalline cellulose, polyvinylpyrrolidone, magnesium stearate and colloidal silica) as the active IMP, supplied in high-density polyethylene bottles closed with high-density screw caps.

ABX464 matching placebo will be manufactured by:

DELPHARM Lille SAS [name] France

Primary packaging labelling as well as Qualified Person release of the IMP are performed at the following site:

SODIA [name]

The study drug requires no specific storage conditions.

6.3. Administration and Dosing

6.3.1. Administration of the investigational product

Subjects will be dosed with a daily dose of 50 mg that is 1 capsule every day.

Subjects will be orally dosed in fed condition (regular breakfast) with 240 mL of water.

A subject diary, in which the subject should report the number of capsules taken and the intake time, will be given to the subject at screening. Moreover, this diary will enable the subject to report also potential discomfort or side effects s/he could experience.

6.3.2. Guidelines for treatment postponement and dose modifications

No intra-subject dose escalation/dose adjustment are allowed.

6.4. Method of Assigning Subjects to Treatment Arms

All subjects will be assigned a unique and incremental subject Identification (ID) number. Subject IDs will be unique (i.e. reallocation of the ID will not be permitted). The format will be a seven-digit number as follows: ABX-country/site number (4 digits) — subject number (3 digits). The latter 3-digit subject number will be assigned according to the subject's order of inclusion in the center.

Eligible subjects will be randomized according to a 2/1 ratio to either an ABX464 or the placebo arm if s/he fulfils all inclusion exclusion criteria.

Randomization will be performed via e-CRF. Treatment numbers will be allocated at once.

Study treatment dispensation will be performed twice at Day 0 (30-capsule bottle; 1 bottle of 50 mg) and at Day 28 (30-capsule bottle; 1 bottles of 50 mg). In all cases, subject should return his/her used and unused bottles at each study visit for a compliance check.

6.5. Blinding and breaking the study blind

Study drug will be packaged in blinded label bottles. Bottles will be numbered according to a randomized treatment number list. The content of the labeling is in accordance with the required references listed in the Good Manufacturing Practices.

The investigator, study personnel, and study participants are blinded with respect to treatment (i.e., active ABX464 or placebo). Sponsor or delegate will generate the random code list and the corresponding treatment number list.

Investigator could have access to unblinding only in case of medical emergency via specific envelopes. However, as there is no antidote it is highly unlikely that knowledge of treatment would affect the clinical management of the subject.

6.6. Packaging

The IMP consists in hard gelatin, powder-filled capsules (size 01) containing 50 mg of ABX464, supplied in high-density polyethylene bottles closed with high-density screw caps.

6.7. Storage

ABX464/Placebo capsules will be shipped to the investigational site at ambient temperature.

No special storage conditions are required.

The IMP should not be used beyond the expiration date. Drug supplies are to be stored in a secure, limited-access location under the storage conditions required by GCP/GMP guidelines.

6.8. Product Accountability

Clinical Study Protocol Study code: ABX464-101

An accurate and current accounting of the dispensing and return of IMP(s) will be maintained on an ongoing basis by the pharmacist and a member of the study site staff in the Accountability Log and case report form and will be verified by the study's monitor.

6.9. Prior and Concomitant Medication

6.9.1. Allowed concomitant treatment

Mandatory and/or allowed Concomitant Medications are:

- ABX464 or its matching placebo administered once daily at 50 mg from Day 0 to Day 56 visit.
- Corticosteroids at stable dose of prednisone or prednisone equivalent ≤20 mg/day during the first 4 weeks of study treatment.
- Oral 5-aminosalicylic acid at stable dose.
- Immunosuppressants in the form of azathioprine, 6-mercaptopurine, or methotrexate at stable dose.
- Antidiarrheals (e.g., loperamide, diphenoxylate with atropine) at stable dose.

Potential other concomitant medications should be kept at constant dose during the course of the study and properly reported in the medical file of the subject and the eCRF.

This information should include the name of the medication (international nonproprietary name), daily dosage, duration, indication and the time of last intake before all PK samplings.

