3. INVESTIGATIONAL PLAN

3.1. Study design

3.1.1. Design and methodology

This Phase IIa study is an 8-week, double-blind, placebo-controlled, randomized study aimed at evaluating the safety and the efficacy of ABX464 given once a day (o.d) at 50 mg in subjects with moderate to severe Active Ulcerative Colitis who have failed or are intolerant to immunomodulators, Anti-TNF α , vedolizumab and/or corticosteroids followed by a one-month follow-up period.

Eligible subjects will be randomized according to a 2/1 ratio in two different groups of treatments according to the following study design.

Upon screening visit (D-14), eligible subjects will be checked for eligibility.

Subject eligibility will be confirmed by the medical staff based of the endoscopy central reading and on the laboratory results performed at screening visit. If eligibility is confirmed, then the subject will be randomized using the eCRF.

At Day 0, study drug (ABX464 or its matching placebo) will be added on top of this background therapy for the next 56 days. ABX464 or its matching placebo will be given once a day at 50 mg.

For subjects receiving oral corticosteroids during the study treatment period, tapering of steroids should start at week 4 at a rate of prednisone or prednisone equivalent 5 mg/week for 4 weeks to discontinuation. However, this study procedure is left to the Investigator's discretion.

The dose of 50 mg of the study drug has been selected based on the reassuring safety data accumulated on the 50 mg o.d. from previous studies and the high exposure in ABX464-NGluc (active metabolite) at this dose.

Eligible subjects will be randomized according to a 2/1 ratio in two different groups of treatments.

Randomization will be stratified according to the following factors: concomitant treatment with corticosteroids and previous TNF antagonist exposure.

Randomized subjects will be seen at the investigational site every week during the first month of treatment and then every two weeks during the second month. Flexible sigmoidoscopy with rectal and/or sigmoidal biopsies will be performed again at week 8.

The DSMB will meet after every 3 subjects are recruited in order to review on a regular basis the safety profile of this dose level and to recommend, if appropriate, the continuation of the study.

The sample size in this Proof of Concept study is 20 subjects receiving ABX464 and 10 subjects receiving Placebo (i.e. a total of 30 subjects).

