6.9.2. Prohibited concurrent medications

The following drugs are prohibited during the course of the study.

- Anti-tumor necrosis factor (TNF) therapies.
- Vedolizumab.
- Topical corticosteroids and topical 5-aminosalicylic acid preparations.
- Cyclosporine and tacrolimus.
- Drugs that could interact with ABX464 should be avoided especially the CYP1A2 substrates. The
 following CYP1A2 substrates with a narrow therapeutic margin are prohibited during the whole course
 of the study (Clozapine, theophylline, ropinirol, warfarin and methadone). Please refer to Appendix #1.
- Use of any investigational or non-registered product within 3 months preceding baseline.

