7.2. Premature trial discontinuation

A subject must be withdrawn at any time from the study for the following reasons:

Subject's premature trial discontinuation could occur for the following reasons:

- Investigator's decision;
- An Adverse Event or an intercurrent condition that preclude continuation of treatment;
 - o Specifically, an increase ≥ 2.0 x ULN in liver transaminases (AST/SGOT and/or ALT/SGPT), in Alkaline phosphatase or in total bilirubin should be considered a treatment discontinuation criterion
- Worsening of the UC defined as a 2-point increase from the screening MCS with 3 days of continuous rectal bleeding confirmed by flexible sigmoidoscopy with an endoscopy subscore of 2 points or higher;
- Major protocol violation;
- Subject's decision;
- · Withdrawal of consent;

A subject who prematurely exits the study for a non-drug related reason, will be replaced (i.e. an additional subject will be randomized and receive the next treatment allocation. This may or may not be the same treatment as the withdrawn subject).

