5 DEFINITIONS

Study Drug: Study drug is taken to mean either ABX464 or placebo.

Baseline: Baseline is defined by patient and by variable as the last non-missing value before the first dose of study drug.

Study Day: Study day is the number of days since start of treatment where the date of first dose is counted as Day 0.

Protocol Deviation: A deviation related to study inclusion or exclusion criteria, conduct of the trial, patient management or patient assessment. This refers to any change, divergence, or departure from the study design or procedures defined in the protocol. Deviations recorded by the Project Manager or

clinical research associate (CRA), or detected by data management or by statistical programming checks will be reviewed and classed as major or minor during the blind Data Review Meeting (DRM) before database lock (DBL).

Major protocol deviations: These are defined as deviations liable to bias the evaluation of the main efficacy endpoint. The following deviations will be considered as major (non-exhaustive list):

- Non-compliance with the inclusion or exclusion criteria;
- Non-compliance with the study treatment;
- · Intake of prohibited medication;
- Non-compliance with time window.

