6.3 PER PROTOCOL SET

The Per Protocol (PP) set is defined as those patients of the FAS population without any major protocol deviation and who completed the study (D56).

The PP set will be used for all efficacy analyses.

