11.3 EFFICACY ANALYSES

Treatment comparisons will be ABX464 vs placebo. The main analysis set for the efficacy analyses will be the PP, and the primary analysis will be repeated for the FAS Set.

Subjects who prematurely terminate the study will be considered failures.

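### In the FAS, a Day 56 completer given new or increased systemic corticosteroid is still scored as a remitter; in the PP set the handling depends on the blind review

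*Protocol*

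**What the plan says.** **Permitted treatment.** Protocol 6.9.1 lists "Corticosteroids at stable dose of prednisone or prednisone equivalent ≤20 mg/day during the first 4 weeks of study treatment" among the allowed medications and adds: "Potential other concomitant medications should be kept at constant dose during the course of the study". Protocol 3.1.1 describes a taper from Week 4 at a rate of "prednisone or prednisone equivalent 5 mg/week for 4 weeks to discontinuation", left to the investigator's discretion. In the prohibited list of Protocol 6.9.2 the only corticosteroid entry is "Topical corticosteroids and topical 5-aminosalicylic acid preparations".

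**Scoring.** Protocol 2.4 and SAP 4.2.1 and 11.3.1 define clinical remission as a Total Mayo Score of at most 2 with no sub-score above 1. SAP 11.3.2 defines clinical response by changes in Mayo points. Neither definition has a medication condition, and Listing 16.2.6 derives remission from the two Mayo checks only. SAP 11.3 gives the sole failure rule: "Subjects who prematurely terminate the study will be considered failures". Protocol 9.2 has the same rule.

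**Withdrawal.** Protocol 7.2 includes "Worsening of the UC defined as a 2-point increase from the screening MCS with 3 days of continuous rectal bleeding", confirmed by sigmoidoscopy with an endoscopy sub-score of at least 2. It also lists investigator's decision and major protocol violation.

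**Analysis sets.** Protocol 9.2 analyses efficacy in the FAS. SAP 11.3 makes the PP set the main efficacy set and repeats the primary efficacy analysis in the FAS. SAP 6.3 limits the PP set to FAS patients who reached Day 56 and had no major deviation. On major deviations SAP 5 says: "These are defined as deviations liable to bias the evaluation of the main efficacy endpoint". Its list is non-exhaustive and cases are classified at a blind meeting.

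**The concern.** The Week 8 comparison is meant to show what ABX464 adds to background therapy. Take a subject on 10 mg of prednisone at Day 0 who flares at Week 5 without a 2-point rise over the screening score. The subject is given 30 mg and has a Total Mayo Score of 2 at Day 56, with no sub-score above 1. No text permits that increase, but none says how it is counted. The stated rules make the subject a remitter for the assigned arm, although the added steroid may explain the remission.

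The situation is foreseeable. Subjects have moderate to severe active disease and have failed or not tolerated earlier therapy, and steroids may be tapered between Weeks 4 and 8. With 20 and 10 subjects per arm, the scoring of one or two people visibly moves the result.

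**Working it through.** **1. Could an existing rule catch the subject?**

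- *Failure for premature termination:* it does not apply to someone who completes Day 56. It can never act in the PP set, which already requires Day 56 completion.
- *UC-worsening withdrawal:* it needs a rise of 2 points over screening. A flare back to the screening level does not meet it. A subject who entered at 11 or 12 on the 0–12 scale cannot meet it, since 11 + 2 = 13.
- *Other withdrawal routes in 7.2:* investigator's decision and major violation could apply, but both are judgements.
- *Intake of prohibited medication:* this is a listed major deviation, but systemic corticosteroid is not on the prohibited list.
- *Non-exhaustive deviation list:* the blind review could exclude the subject from the PP set. That removes the subject from the denominator; it does not count a failure.
- *Data review meeting:* SAP 9.4 has it discuss imputations for the primary endpoint, while SAP 10.2 says nothing is imputed. No scoring rule is written.

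So the FAS credits the subject, and the PP set credits or excludes.

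**2. The plan's own power.** Inputs from Protocol 9.4: 60% vs 20%, 20 vs 10 subjects, one-sided 10%, normal approximation.

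Power = Φ{[p1 − p2 − z0.90 √(p̄(1 − p̄)(1/20 + 1/10))] / √(p1(1 − p1)/20 + p2(1 − p2)/10)}, with p̄ = (20p1 + 10p2)/30.

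p̄ = 14/30 = 0.467. The null term is 1.2816 × √(0.2489 × 0.15) = 0.248. The denominator is √(0.012 + 0.016) = 0.167. Power = Φ[(0.400 − 0.248)/0.167] = 81.9%, against a stated 81%.

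**3. Power under assumed crediting.** No rescue rate is in the documents. For rescue in both arms, each rate becomes p + (1 − p)r, where r is the share of non-remitters credited.

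- r = 2% in both arms (60.8% vs 21.6%): 80.2%
- r = 5% in both arms (62% vs 24%): 77.7%
- r = 10% in both arms (64% vs 28%): 73.5%
- placebo only, plus 5 points (60% vs 25%): 72.0%
- placebo only, plus 10 points (60% vs 30%): 61.2%

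**4. Single subjects.** One-sided signed-root likelihood ratio test, unstratified (the planned test is stratified), with G = 2 Σ O ln(O/E). For 12/20 vs 2/10 the expected counts are 9.33, 10.67, 4.67 and 5.33. Then G = 2(3.016 − 2.301 − 1.695 + 3.244) = 4.527, √G = 2.128 and p = 0.017.

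With one rescued placebo subject:

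- scored as failure, 12/20 vs 2/10: p = 0.017
- excluded from the PP set, 12/20 vs 2/9: G = 3.713, p = 0.027
- credited, 12/20 vs 3/10: G = 2.451, p = 0.059

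Two credited placebo subjects, 12/20 vs 4/10: G = 1.075, p = 0.150.

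In the other direction, one extra ABX464 remitter takes 8/20 vs 2/10 (p = 0.131) to 9/20 vs 2/10 (p = 0.084).

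**5. Over all outcomes at 60% vs 20%.** Enumerating both binomials with the same test gives significance in 85.2% of trials. If every trial had one credited placebo remitter, significance would be lost in 16.9%. If every trial had one credited ABX464 remitter, it would be gained in 5.4%.

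**The case against.** The strongest reply is that rescue already departs from the protocol: 6.9.1 allows only stable, low-dose steroid. Added steroid before a remission assessment fits the definition of a major deviation, so the blind review can remove the subject from the SAP's main efficacy set, or the investigator can withdraw the subject, who then counts as a failure in the FAS. The review is blind and precedes database lock, so results by arm cannot steer it. This stands. A reader might infer that every rescued completer enters the main result as a remitter; the documents do not support that. What remains is the FAS, and a PP outcome that no rule fixes in advance.

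The second reply concerns weight. Remission is a secondary endpoint in a 30-subject proof-of-concept study whose primary endpoint is TEAEs. The fall to 61.2% needs 1 in 8 placebo non-remitters (10 of 80 points) to be rescued, kept on study and brought to remission including endoscopy, and none on ABX464. The 16.9% and 5.4% assume such a subject in every trial. This also stands: the figures show sensitivity, not expected impact. In the single-subject example all three p-values stay below 0.10.

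Third, counting remission regardless of rescue is a legitimate treatment-policy choice. It is, but neither document states that choice, and the plan already scores dropouts as failures.

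**Conclusion.** The point holds as a gap in scoring. In the FAS, following the text exactly credits a rescued Day 56 completer to the assigned arm. In the PP set the text leaves credit or exclusion to case-by-case classification. Clinical response has the same gap, although the SAP tabulates response for the PP set only (Table 14.2.2.5).

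The size cannot be stated, because the rescue rate and its split by arm are not in the documents. Prescribers are blinded, so if the drug works, more rescue on placebo is likelier, and with it dilution of the difference.

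Two stronger readings should be resisted. One is that the sample size is wrong or true power is 61%: the stated 81% reproduces, and the lower figures rest on assumed crediting. The other is that the gap inflates false positives: that would need more credited rescue on ABX464, and nothing in the documents points to such an imbalance under blinding. The matter is worth settling before unblinding because it is cheap and the arms are small, not because a material bias has been shown.

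**What to change.** - **FAS scoring (SAP 11.3, 11.3.1, 11.3.2).** Count as a non-remitter and non-responder any subject who, between Day 0 and the Day 56 assessment, starts a systemic or oral corticosteroid for UC, raises it above the Day 0 dose, or starts or raises another UC treatment as rescue. Include the oral beclomethasone and budesonide MMX named in Protocol 4.2.1. Measure against the Day 0 dose, so that going back up after a taper, to no more than that dose, is not a failure. Keep early termination as failure.
- **PP set (SAP 5).** Name such rescue as a major deviation, so that exclusion is fixed in advance. Keeping these subjects in the PP set as failures would conflict with its definition.
- **Output.** Add a rescue flag to Listing 16.2.6, and report remission scored regardless of rescue as a sensitivity analysis.

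The cost is SAP wording, one derived flag and one extra table. Protocol 6.9.1 already has drug name, daily dosage, duration and indication reported in the eCRF, so no new data are needed and subject care is unchanged. The downside is that remission rates may be slightly lower, and the FAS estimate becomes a composite (remission without rescue) instead of a treatment-policy effect. If the sponsor prefers treatment policy, the SAP should say so and give the composite as the sensitivity analysis.

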6.9.2. Prohibited concurrent medications

The following drugs are prohibited during the course of the study.

- Anti-tumor necrosis factor (TNF) therapies.
- Vedolizumab.
- Topical corticosteroids and topical 5-aminosalicylic acid preparations.
- Cyclosporine and tacrolimus.
- Drugs that could interact with ABX464 should be avoided especially the CYP1A2 substrates. The
 following CYP1A2 substrates with a narrow therapeutic margin are prohibited during the whole course
 of the study (Clozapine, theophylline, ropinirol, warfarin and methadone). Please refer to Appendix #1.
- Use of any investigational or non-registered product within 3 months preceding baseline.

7. SUBJECT COMPLETION AND WITHDRAWAL

7.1. Subject Completion

Treatment with ABX464/Placebo shall continue until Day 56 visit, except if a subject fulfils a premature discontinuation criterion (defined below). After Day 56, subjects are willing to carry on the study treatment will be able to take part in an open-label study (ABX464-102).

In any other case, the subjects will exit the study (EoS) and will be treated according to the standard of care. The ABX464-102 follow-up study is a separate clinical protocol subject to health authorities and ethics committee approvals.

7.2. Premature trial discontinuation

A subject must be withdrawn at any time from the study for the following reasons:

Subject's premature trial discontinuation could occur for the following reasons:

- Investigator's decision;
- An Adverse Event or an intercurrent condition that preclude continuation of treatment;
 - o Specifically, an increase ≥ 2.0 x ULN in liver transaminases (AST/SGOT and/or ALT/SGPT), in Alkaline phosphatase or in total bilirubin should be considered a treatment discontinuation criterion
- Worsening of the UC defined as a 2-point increase from the screening MCS with 3 days of continuous rectal bleeding confirmed by flexible sigmoidoscopy with an endoscopy subscore of 2 points or higher;
- Major protocol violation;
- Subject's decision;
- · Withdrawal of consent;

A subject who prematurely exits the study for a non-drug related reason, will be replaced (i.e. an additional subject will be randomized and receive the next treatment allocation. This may or may not be the same treatment as the withdrawn subject).

